There are minimal risks to be incurred from participating in this study. Specific risks related to the clinical and cognitive assessments (study questionnaires) and tDCS are described below. Participants may be uncomfortable sitting or lying for an extended period of time on the chair, recliner or stretcher due to their CLBP.

Risks and discomforts due to Clinical and Cognitive Assessment Administration:

There are several questionnaires that the participant will be asked to answer. The time it takes to answer these questions may create frustration or fatigue. Answering the clinical symptom rating questions may involve sensitive information that could cause emotional reaction, embarrassment or discomfort. Previously undisclosed or unknown mental health problems may be identified.

Risks due to tDCS:

There is some inherent risk with tDCS. Mainly there is a risk of skin irritation where the electrodes are attached to the scalp, which in the literature has been mostly limited to transitory redness. No toxic effects have been found, and the procedure carries few risks (Brunoni, et al., 2012). At the levels we are proposing, only a few publications report minor injuries, and the stimulation is widely considered to be “safe” (Bikson, et al., 2009). In rare cases, when skin around stimulation sites was non-intact, or when the stimulation was delivered for a long time without proper conductive solutions being applied to the electrodes, a few minor burns and skin lesions have been observed (Frank, et al., 2010). If electrodes/sponges are placed over preexisting skin lesions, such as vascular moles and angiomas there may be a greater conductance than the surrounding skin, increasing the risk of irritation or possible burns. Care is thus taken to exclude potential participants who exhibit broken or marked skin near the sites of the electrodes. The electrodes in this study are soaked in normal saline. A study using the same amperage proposed in this protocol found no mood or cognitive changes due to tDCS (Iyer, et al., 2005). Transient, very rare post-tDCS effects have been found to include mild headaches, nausea, and insomnia (Poreisz, et al., 2007).

PROTECTION OF THE SUBJECT

Participants will be reminded that they may stop participating in the study at any time for any reason without affecting their VA health care or relationship with PVAMC.

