Participants will be encouraged to take breaks when needed. They will be reminded that they may refuse to answer any questions on the study questionnaires and they may stop the tDCS treatment session at any time.

Management of Risk due to due to Clinical and Cognitive Assessment Administration

[name] and/or [name] will be available to address any mental health concerns and assist in appropriate referrals as needed. As noted above participants may refuse to answer any questions and take breaks as needed.

Management of Risks due to tDCS.

Further Background information and precautions related to risk

Direct Current (DC) polarization has been applied unilaterally to the primary motor and dorsal prefrontal areas in many studies over the past decade (Wassermann, 2008) with no reports of adverse effects attributable to effects on the central nervous system. The proposed stimulation intensity in this study is similar to the stimulation intensity used in previous protocols as also performed at the NIH (and for which the risk determination from the FDA was requested). No adverse side-effects have been reported in these previous studies with the proposed stimulation settings. The proposed intensity level is therefore at the level at which we will expect to find effects of tDCS on our behavioral output measure, but without causing adverse side-effects. In a study measuring thermal effects of tDCS using a MRI-derived finite element human head model conventional rectangular-pad (7 times 5 cm²) and HD-tDCS using the ring (4 times 1) electrode configurations were compared using a bio-heat model. The results indicate that clinical tDCS

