does not increase tissue temperature and the 4 x 1 configuration leads to a negligible increase in scalp temperature (Datta et al., 2009). In safety studies conducted at City College of New York (CCNY) and during usage at the National Institutes of Health (NIH), sets of these electrodes did not cause skin problems more serious than tingling and transient redness when applied to the skin of the arm with current densities up to 2.56 mA/cm² and durations of up to 22 minutes ([name], personal communication). It was also found that cathodal current produced the most skin irritation. However cathodal stimulation will be of crucial importance to our study design as we hypothesize that our target brain areas may be overactive, and hence require suppression. During cathodal stimulation we will take extra precautions that consist of instructing the participants to advise the research staff of any discomfort during testing, inspection of stimulation sites as needed and immediate discontinuing stimulation if discomfort occurs.

The tDCS device that will deliver the direct current is adjustable in both intensity as well as duration of stimulation. In addition, the device will be 9V battery-driven to function as a constant current stimulator with a maximum output in the milliamps range with absence of the risk of sudden large intensities of electrical current that could occur with an electrical driven device.

Prolonged passage of direct current across metallic electrode (where electrons from the stimulator are converted to ions carried through the body) can produce undesired electrochemical products such as pH changes. The sponge pocket will act to physically separate, and thus buffer, the skin from electrochemical changes. The normal saline used on the sponges assists in preventing burns. In addition, electrodes/sponges will not be placed over cuts, or skin lesions such as vascular moles and angiomas that might have greater conductance than the surrounding skin. One set of sponges will be used throughout the study for each participant. Electrodes will be held in place by using special head bands made of flexible rubber.

All participants will be carefully screened prior to tDCS for contraindications to tDCS (see exclusion criteria). At least one PI will be available on an immediate basis for all study treatment sessions.

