tDCS will be administered by the tDCS Operator - a trained and qualified individual supervised the principal investigators to deliver, or assist in delivery of, tDCS. Training includes the knowledge of safety considerations and precautions associated with tDCS.

The tDCS operator will:

- a) Assess the participants' scalp skin where the electrodes will be placed to assure it is intact,
free of lesions, cuts or exclusionary skin disorders.
- b) Prepare and position the electrodes and tDCS device on the participant for accurate brain stimulation according to the protocol prior to initiation of stimulation.
- c) Operate the hardware associated with the tDCS device to assure the level of current and amount of time is accurate per protocol.
- d) Administer the tDCS, at the parameters established by the tDCS Attending Physician as per identified in this protocol.
- e) Assess the participant's mental status and general clinical condition before and after tDCS

to assure the safety of the participant to have tDCS and the safety of the participant to return home.

f) Monitor the participant during the tDCS session to assess for potential occurrence of adverse events.

g) Make routine adjustments to the placement of the device as required and consistent with product labeling (e.g., to ensure contact between participant's head and electrode) during the tDCS session. The tDCS Operator may not independently make any revision to pre-determined stimulation dose or electrode position parameters prescribed by the study protocol.

h) Determine if tDCS should be interrupted or terminated (e.g., participants express increasing discomfort to their skin under the electrodes; participants show signs of discomfort or other stress; participant wants to discontinue study procedures).

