i) Take action in accordance with established VA regulations in case of adverse events, for example: he/she will seek immediate medical attention for the participant if necessary; if there is any doubt about the mental or physical status of a participant after testing he/she will consult with the available study physician. He/she will document and report all adverse events (e.g. skin lesion or significant skin discomfort) to the principal investigators. A study physician will evaluate the participant and make a recommendation for immediate or follow-up care if required. Telephone or in-person follow-up will be arranged as needed. Any participant judged on clinical grounds to have suffered adverse effects will thus be evaluated and treated as necessary and withdrawn from the study.

j) When not in use, assure the tDCS machine, electrodes, sponges, conductive gel, alcohol prep pads and normal saline are maintained in the secure location as assigned to [name] in Building 1 or 32, in a locked cabinet in a lockable room.

Management of Risks to Confidentiality:

This study will be conducted in compliance with Good Clinical Practice procedures. Strict standards of confidentiality will be maintained. Precautions will be taken to prevent disclosure of information to unauthorized parties.

All paper records, forms and data will be stored in secure files to which only members of the investigative team will have access. Computer records will be protected by standard measures that limit access of the data to designated trained research project personnel.

This research data will include participant information that may be of a sensitive nature. All patient data will be stored in locked files in lockable offices. Computers with subject data will be password protected and encrypted to ensure confidentiality of patient records. Specifically:

(1) Data sheets will be stored in one of the Principal Investigators' locked files in a locked office as assigned at the Providence VA Medical Center); (2) Data will be entered in coded form; (3) Data will be stored in computer files protected from unauthorized access by passwords; (4) Information that might potentially allow an individual participant to be identified will not be allowed in any publications, or reports sent to individuals outside the study; and (5) All

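### The adverse-effects rule removes participants from the study, not only from stimulation, and nothing visible keeps their later questionnaires: an avoidable loss, probably small and of unknown sign

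*Combined protocol and SAP*

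**What the plan says.** Item i) of the tDCS operator's duties, under Management of Risks due to tDCS, states: "Any participant judged on clinical grounds to have suffered adverse effects will thus be evaluated and treated as necessary and withdrawn from the study". The rule covers every such participant, and what they leave is the study.

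The protocol treats stopping stimulation as a separate matter. Item h) has the operator "Determine if tDCS should be interrupted or terminated", and Further Background information and precautions related to risk calls for "immediate discontinuing stimulation if discomfort occurs". Neither mentions leaving the study.

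The only later contact named in item i) is "Telephone or in-person follow-up will be arranged as needed". It follows a sentence about a study physician recommending care, so in context it is clinical follow-up.

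Table 1 and Study Visits place WHYMPI, PASS-20 and RMDQ at session 1 (baseline), session 5, session 10 and the six-week phone call. The call repeats the session 10 measures and is timed from the last stimulation session. Material Inducements deals with early withdrawal only as a matter of payment. Data Analysis lists (M)ANOVA, repeated-measures and mixed models, with no analysis set and no rule for missing data.

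**The concern.** Hypotheses 1.1, 1.2, 2.1 and 2.2 rest on scales with three post-baseline assessments. A participant withdrawn in sessions 1 to 4 contributes none of them. One withdrawn between sessions 5 and 10 loses session 10 and the six-week call.

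This loss happens after randomisation, so randomisation does not protect against it. It may be related to treatment: active delivers up to 2 mA for 20 minutes, while sham delivers 40 seconds at 1 mA and then almost nothing. It may also be related to outcome, if those withdrawn would have scored differently from those who stayed. With 20 per arm, each participant is 5% of an arm, and an outcome never collected cannot be recovered at analysis.

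**Working it through.** **Inputs.** From the documents: 20 per arm (Study Population), the assessment times and the two stimulation doses. Not given: withdrawal rate, score gap, SD, alpha and power. Everything below is therefore in SD units under stated assumptions, and there is no figure of the plan's own to reproduce.

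**Expected harms.** The protocol says of skin irritation "which in the literature has been mostly limited to transitory redness", of systemic effects "Transient, very rare post-tDCS effects have been found to include mild headaches, nausea, and insomnia", and of earlier studies "No adverse side-effects have been reported in these previous studies with the proposed stimulation settings". This suggests few withdrawals but gives no rate. For assumed rates of 1%, 2%, 5%, 10% and 20% in an arm of 20, the expected number is 0.2, 0.4, 1, 2 and 4. The chance of at least one, 1 − (1 − rate)^20, is 18%, 33%, 64%, 88% and 99%.

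**Dose by arm, per session.** Active: at most 2 mA × 1200 s = 2400 mC. Sham: 1 mA × 40 s + 0.002 mA × 1160 s = 42.3 mC. This is a difference in dose, not a tolerability rate.

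**Complete-case bias.** Let k be the number lost in an arm and g the gap in SD (withdrawn minus retained, higher score = worse). Bias in favour of active = (k_active × g_active − k_sham × g_sham) / 20. With |g| at most 1, each participant lost adds at most 1/20 = 0.05 SD.

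| Lost, one arm | gap 0 | gap 0.5 SD | gap 1 SD | gap 1 SD, in standard errors |
|---|---|---|---|---|
| 1 | 0 | 0.025 | 0.05 | 0.16 |
| 2 | 0 | 0.05 | 0.10 | 0.32 |
| 4 | 0 | 0.10 | 0.20 | 0.63 |

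The standard error of the arm difference is √(2/20) = 0.316 SD. The sign reverses if the losses are in sham instead of active, and also if those withdrawn would have scored better than those retained.

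**Precision.** With the losses in one arm, the standard error becomes √(1/(20 − k) + 1/20): 0.320, 0.325 and 0.335 for k = 1, 2 and 4, an increase of 1.3%, 2.7% and 6.1%.

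**Mixed model.** Take baseline, session 5 and session 10 with equal correlation ρ, baseline modelled as a response, one lost and a session 10 gap of 1 SD. Withdrawn before session 5, the bias is 0.05 × (1 − ρ × baseline gap). Withdrawn after session 5 with a 1 SD gap there too, it is 0.05 × (1 − [ρ/(1 + ρ)] × (baseline gap + 1)).

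| Withdrawn | Baseline gap | ρ = 0.5 | ρ = 0.7 |
|---|---|---|---|
| before session 5 | 0 | 0.050 | 0.050 |
| before session 5 | 1 SD | 0.025 | 0.015 |
| after session 5 | 0 | 0.033 | 0.029 |
| after session 5 | 1 SD | 0.017 | 0.009 |

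The model helps to the extent that baseline and session 5 scores predict the gap. Before session 5 it gives no help if baselines are equal.

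**Larger arms.** Appendix B adds data from a parallel study, number not given. With an assumed 30 or 40 per arm, each participant lost adds at most 1/30 = 0.033 or 1/40 = 0.025 SD, against standard errors of 0.258 or 0.224.

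**The case against.** The strongest reply is that this hardly matters. The study is declared exploratory and is pilot-funded, harms are expected to be rare and mild, ordinary discomfort is met by stopping stimulation, and withdrawal needs a clinical judgement. One participant lost moves the estimate by at most 0.16 of a standard error, and even four stay below one standard error. All of that stands, and it limits the size of the point. It does not justify discarding outcomes of randomised participants when keeping them costs so little.

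Nor is the loss wholly avoidable. Participants may leave at any time, someone just harmed may decline further contact, and the VA rules and consent terms that apply cannot be seen here.

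Four stronger readings are tempting, and the documents do not support them:

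- A reader might infer that the rule favours active. That requires the losses to fall mainly on active and those withdrawn to have scored worse. Someone withdrawn for a scalp lesion need not have worse pain distress.
- A reader might take "It was also found that cathodal current produced the most skin irritation" as evidence that active will lose more. The sentence does not compare active with sham, and the sham current also runs between an anode and a cathode. Only the dose difference points towards active.
- A reader might apply the broad definition in Adverse Event Reporting, which includes a pre-existing condition getting worse, and expect many withdrawals, including sham participants with worse back pain. Item i) is triggered by adverse effects found on clinical judgement, in a section on tDCS risks, with skin problems as its examples. The broad reading is possible but doubtful.
- A reader might conclude that a mixed model cannot help before session 5. That holds only if those withdrawn match completers at baseline.

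**Conclusion.** The point holds as a cheap improvement. Followed as written, item i) ends the study for a participant in whom stopping stimulation would suffice, and no visible text keeps the outcomes that follow. The loss comes after randomisation and may be related to treatment or outcome. Active may lose more because its dose is higher, but no withdrawal rate is given.

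The effect is probably small and its sign is unknown. The complete-case bounds rest on assumed arms of 20, an assumed number lost and an assumed gap of at most 1 SD; if the gap is zero, so is the bias. That the size is small is a judgement from the protocol's description of harms. The documents do not show that any conclusion of the trial would change.

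**What to change.** In item i), change the consequence from leaving the study to leaving further stimulation. Then add the following, to apply unless the participant withdraws consent and subject to VA rules and the consent terms:

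- Collect the session 5 and session 10 questionnaires on their planned dates, in person or by phone.
- Make the six-week call about six weeks after the planned session 10. Counted from the last stimulation, someone stopped at session 1 on a Monday would be called 11 days early (Monday of week one to Friday of week two). This is a minor adjustment, since the timing is only approximate.
- Use a blinded rater who is not told of the stop.
- Analyse these participants in their assigned arm with the mixed model already listed, and report stimulation stops by arm, session and reason.

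The clinical rules for stopping stimulation stay unchanged. The questionnaires, blinded staff and phone call already exist, so the cost is protocol and consent wording plus up to three questionnaire sets per affected participant. The downsides are some phone data at sessions 5 and 10, some participants declining, and a small risk that an off-schedule contact unblinds the rater.

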Appendix A: Social Media Recruitment

A. Language for Online Posting Sites (i.e. Facebook and/or Craigslist) – Volunteers

Needed for a Study of Veterans with Chronic Low Back Pain We are looking for Veterans with chronic low back pain to participate in an 11 day research study at the Providence VA Medical Center. This study is looking at whether or not small amounts of electricity applied to the head may be able to change the way one feels about their chronic pain.

The study involves 11 study visits at the PVAMC, the first to see if you are eligible, followed by 10 study treatments. A follow-up phone call is also placed several weeks after the study treatments are completed. During study visits, participants will undergo a low level electrical current through their head for 20 minutes and will be asked to answer questions about pain, mood, sleep, and well-being. Some participants will not receive the actual treatment and participants will not know if they are assigned to this group.

Participants will receive gift cards of up to \$100, \$10 value for every treatment session attended, for their time and effort.

For your own security, please do not comment with any of your personal or health information, call [contact] [name] or [name] and arrange for a secure means to share such information in response to this post.

B. Language for Twitter (140 character limit)

Are you a Veteran with chronic low back pain? You may qualify for a research study at PVAMC. Call [contact] [name] for more info.

Appendix B- inclusion of de-identified data from Butler Hospital

There is an IRB approved parallel study at Butler Hospital, in Providence RI. De-identified data from this study will be included in the analysis of this study. Sharing of this de-identified data has been approved by the Butler IRB. This de-identified data will be entered into the study's data capture excel spreadsheets stored on \\R04pronas21\research_protocols\ [name] \tDCS-CLBPR and analyzed by the study statistician and research staff.

The Investigator will send a copy of the Butler data to his VA email account. The Investigator will then upload and co-mingle the Butler data with the existing data located above. There is no expectation of return of the data.

There is no additional software or web access needed.

The data flow is amended to include the additional data from Butler detailed above.

There will be no hard drives on this study.

The storage location will remain the same.

There will be no removal of sensitive data from the VA environment.

No storage of data outside the VA environment.

The data transmission will be an email of de identified data one way one time to append the data base at the VA Medical Center.

No shipping will be required

No data return is expected.

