tDCS for Chronic Low Back Pain: A Study Examining the Effect of Transcranial Direct Current Stimulation on the Emotional Response to Chronic Low Back Pain

Principal Investigator:

[name]., Ph.D.

STUDY DESCRIPTION

The goal of this study is to investigate the role of central neural pathways in mediating chronic pain. The aim of the study is to test the effect of stimulating brain regions that are part of a network underlying central pain processing using a non-invasive brain stimulation technique, transcranial Direct Current Stimulation (tDCS). Prior studies have used tDCS to target both sensory related cortical areas (Fregni 2006) and those important for higher-order representations of pain (Mendonca 2011). This study will target brain regions important for the behavioral response to the chronic sensation of pain. The hypothesis is that stimulation of these brain regions can modulate not only the affective component of pain, but ultimately also improve functioning and quality of life. This hypothesis will be tested by treating study participants eighteen and older with chronic low back pain (CLBP) of greater than six months using tDCS. To be part of this study, participants must be Veterans that meet all the inclusion and exclusion criteria.

Specific Aims:

The aim of the proposed study is to determine effects of tDCS on the affective and behavioral component of chronic pain. The study will specifically target the dorsal anterior cingulate cortex (dACC), an important component of brain circuits that mediate learning in response to emotionally charged experiences. Measures of distress will be obtained due to the sensory component of pain to assess the degree to which pain interferes with the participants' daily activities and the emotional impact of CLBP on their lives.

Aim 1

To test the acute effects of active vs. sham cathodal (inhibitory) tDCS over dorsal anterior cingulate cortex (dACC), a region implicated in the affective components of pain in forty (40) patients in a controlled design.

Aim 2

To test the longer term effects of active vs. sham cathodal (inhibitory) tDCS over dACC in the same forty (40) patients in a controlled design.

Hypotheses:

Acute effects:

Hypothesis 1.1:

Distress associated with pain as measured by the West Haven-Yale Multidimensional Pain Inventory (WHYMPI) (affective subscale) and pain anxiety symptom scale (PASS-20) will decrease after ten (10) days of active, but not sham stimulation.

Hypothesis 1.2:

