Transcranial direct current stimulation, or tDCS, is classified by the FDA as a minimal risk technique. tDCS applies low amplitude direct current to the scalp to modulate the excitability of underlying cortex. Several studies have shown promising results treating acute pain, neuropathic pain resulting from spinal cord injury, and chronic pain from fibromyalgia (Antal 2008; Lefaucher 2008; Fregni 2006). As in these studies, tDCS will be used to target areas of the brain that participate in pain processing at higher levels beyond simply relaying sensory information. By changing activity in the “affective tier” of brain networks implicated in responses to pain, the investigators expect to modify emotional responses and behaviors that add to its burden.

STUDY POPULATION

To be eligible for participation in this study participants must be eighteen years or older with a diagnosis of CLBP chronic low back pain and meet the inclusion and exclusion criteria (see below). There are no exclusions based on race, ethnicity or gender. The plan is to consent up to fifty (50) volunteers with a goal of enrolling forty (40) participants, twenty (20) in the treatment group and twenty (20) in the control group. Only Veterans recruited from the Providence VA Medical Center (PVAMC) will be allowed to enroll.

Inclusion Criteria:

1. At least eighteen (18) years old;

2. Chronic Low Back Pain - must be present for ≥ 6 months duration in the lumbar region, present more than half the days of the month, and on average be at a moderate level of severity in the last month (≥ 4 on the DVPRS scale of pain intensity from 0 (no pain) to 10 (worst pain imaginable).
3. At least one trial of physician recommended medication (i.e. acetaminophen, NSAIDS, skeletal muscle relaxants)
4. Pre-existing opioid and non-opioid pain medication must be non-existent or stable (medications have not changed for one month)
5. Be able to understand, read and write English.
6. If female and of childbearing age, agree to use acceptable birth control during the study treatment period (oral contraceptives, history of tubal ligation, history of a hysterectomy, or a reliable barrier method) during the study treatment period.

Exclusion Criteria:

1. Lifetime DSM-IV diagnosis of bipolar disorder, schizophrenia, or other chronic psychotic condition;
2. Current DSM-IV diagnosis of substance dependence for alcohol, sedative/ hypnotic drugs, stimulants, or cocaine;

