Screening is expected to take approximately one and a half (1 ½) to two hours (2). The principal investigator/s will make the ultimate determination of whether the participant meets all the enrollment criteria and is appropriate to enter the study. Participants that do not meet the study criteria will be informed that based on the information collected, it has been determined they are not appropriate for the current study. Appropriate referrals will be made to other health care providers, at the VA or to outside providers, if desired by the participant.

RESEARCH PLAN

After the potential participant signs the consent form, is screened, found eligible and states they are still interested, they will be enrolled into the study. The study includes a screening visit, ten (10) study treatment session visits on consecutive weekdays and a follow-up phone call, approximately six (6) weeks after the last study visit. The ten study visits will occur at the

PVAMC and will take approximately one (1) to one and a half hours (1 ½) hours. The follow-up phone call will take about one (1) hour. The total duration of this study for the participant is expected to be approximately eighteen (18) hours; this includes the consent process, screening and eligibility assessments, and ten research visits which will include the study treatment, tDCS, completion of study related questionnaires, and the follow-up phone call.

Half of the participants will receive only sham stimulation for all treatment days (days where tDCS is applied) and half will receive only active stimulation; this will be randomly assigned. Comprehensive measures of distress resulting from CLBP will be administered to assess both the short and longer term effects of tDCS treatment. Participants and research staff administering outcome scales will be blinded to active vs. sham tDCS.

Specific Procedures:

Questionnaires

Table 1, below identifies the schedule for when the study questionnaires will be used. All questionnaires will be done with assistance of blinded study personnel.

Pain Severity:

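### Appendix B pools Butler Hospital data into a trial whose aims concern forty PVAMC Veterans, but the analysis plan requires neither a within-study treatment comparison nor a VA-only estimate

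*Combined protocol and SAP*

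**What the plan says.** Aim 1 is set in forty patients, and Aim 2 tests longer-term effects "over dACC in the same forty (40) patients in a controlled design". STUDY POPULATION plans 20 in the treatment group and 20 in the control group, and adds: "Only Veterans recruited from the Providence VA Medical Center (PVAMC) will be allowed to enroll". RESEARCH PLAN assigns treatment at random: "Half of the participants will receive only sham stimulation for all treatment days", and the other half only active stimulation.

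Appendix B then brings in a second source: "There is an IRB approved parallel study at Butler Hospital, in Providence RI". Its instruction is firm: "De-identified data from this study will be included in the analysis of this study". On handling, it says: "The Investigator will then upload and co-mingle the Butler data with the existing data located above". The transfer is a single email, "one way one time to append the data base at the VA Medical Center". Beyond the word parallel, nothing is said of Butler's size, eligibility, randomisation, allocation or visit schedule.

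DATA ANALYSIS lists families of linear model (ANOVA and MANOVA, repeated measures, mixed models), then post-hoc comparisons of conditions. It does not mention Butler, a study or site factor, a study-by-time term or a separate VA estimate. No other section supplies them.

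**The concern.** Two things follow if the text is carried out as written.

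First, the analysed group differs from the group in the aims, whatever Butler looks like. A reader of the results could not tell whether an effect belongs to the forty PVAMC patients or to the merged set.

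Second, nothing requires active patients to be compared with sham patients from the same study. Randomisation protects the comparison inside the VA trial. It does not protect a comparison of VA sham patients with Butler active patients. If the arms of the merged set contain different proportions of Butler patients, any difference in average change between the studies becomes part of the apparent treatment effect.

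The hypotheses are about change; Hypothesis 1.1, for example, says that distress "will decrease after ten (10) days of active, but not sham stimulation". The questionnaires are given at sessions 1, 5 and 10 and at follow-up. In a repeated-measures model the relevant term is therefore group-by-time, and a study main effect alone does not protect it.

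**Working it through.** **Plan's own figure.** There is none to reproduce: DATA ANALYSIS states that there is no power analysis.

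**Inputs.** From the documents: VA 20 active and 20 sham. Assumed, because the documents give nothing: Butler n = 20 split 10/10, 12/8 or 15/5 (active/sham); visit SD 1 and correlation between visits 0.5, so the SD of change is √(2 × (1 − 0.5)) = 1; no true treatment effect; two-sided 5% level; studies differing by 0.8 SD in mean change.

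**Step 1: bias with study ignored.** Bias = (study difference in change) × (Butler share of active arm − Butler share of sham arm).
- 10/10: 0.8 × (10/30 − 10/30) = 0.
- 12/8: 0.8 × (12/32 − 8/28) = 0.071 SD.
- 15/5: 0.8 × (15/35 − 5/25) = 0.183 SD.

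At a difference of 0.4 SD these halve to 0, 0.04 and 0.09 SD. With Butler n = 40 and 0.8 SD, they are 0 at 20/20; 0.8 × (24/44 − 16/36) = 0.081 at 24/16; and 0.8 × (30/50 − 10/30) = 0.213 at 30/10. Outside this range, a single-arm Butler study (20/0) differing by 1 SD would give 1 × (20/40 − 0) = 0.50 SD and type I error of about 39%.

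**Step 2: simulated bias and type I error, Butler n = 20, difference 0.8 SD.** The repeated-measures rows use four visits, a random intercept, extra Butler change of 0.4, 0.8 and 0.8 SD at the three later visits, and the session-10 group-by-time term (6,000 trials per split). The change-score row uses 40,000 trials and the baseline-adjusted row 5,000.

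| Analysis | Bias (SD): 10/10, 12/8, 15/5 | Type I error: 10/10, 12/8, 15/5 |
|---|---|---|
| Change score, study ignored | 0.000, 0.072, 0.181 | 0.036, 0.043, 0.082 |
| Baseline-adjusted, study ignored | 0.001, 0.073, 0.183 | 0.036, 0.042, 0.093 |
| Repeated measures, study main effect only | −0.001, 0.068, 0.185 | 0.042, 0.054, 0.096 |
| Repeated measures, study and study-by-time | −0.001, −0.004, 0.002 | 0.048, 0.053, 0.052 |

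With study as a factor in the change-score or baseline-adjusted model, absolute bias is at most 0.002 and type I error 0.048-0.053. At a 0.4 SD difference with study ignored, type I error at 15/5 is 0.059 (change score) and 0.057 (baseline-adjusted). A stable difference in level between studies, with no difference in change, does not bias the group-by-time or change analysis.

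**Step 3: price of adjusting.** The information on the treatment effect is (active × sham)/(active + sham), taken over the whole pool or summed within study.
- Pooled: 30×30/60 = 15.00; 32×28/60 = 14.93; 35×25/60 = 14.58.
- Within study: 10 + 5 = 15.00; 10 + 4.8 = 14.80; 10 + 3.75 = 13.75.
- Standard error, adjusted over pooled, √(pooled/within): 1.000, 1.004, 1.030.
- Standard error, VA-only over adjusted, √(within/10): 1.225, 1.217, 1.173.

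**Step 4: treatment-by-study term.** Its standard error is √(1/10 + 20/(active × sham)), using the Butler counts: 0.548, 0.555 and 0.606 SD. Power for a 0.5 SD interaction is 13-15%. If it sat in the main model and the two studies were averaged equally, the treatment variance would be ¼ × (0.1 + 20/(active × sham)) = 0.0750, 0.0771 and 0.0917. Against the study-adjusted model (1/15.00, 1/14.80, 1/13.75) the standard error rises by 6%, 7% and 12%. Against the unadjusted pool it rises by 6%, 7% and 16%.

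**The case against.** The strongest reply is that the bias rests wholly on assumption. Butler is called parallel, and this trial allocates half to each arm, so an equal split is plausible. In that case the unadjusted pool is unbiased and the test errs on the cautious side (about 4% against 5%). Type I error clearly above 5% needs a strongly unequal split such as 15/5, and 8-10% also needs a difference of 0.8 SD in change. The VA-only standard error is √(1/10) = 0.32 SD, so most of the biases illustrated for a randomised Butler study are small beside sampling error. All of this stands.

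It is also fair that DATA ANALYSIS names no model term of any kind, that the study is labelled exploratory, that a mixed model could hold a study factor, and that Appendix B reads mainly as a data-security text whose analytic silence is weak evidence of intent. Butler's design may be described in its own protocol, and nothing says that study of origin will be dropped. These points lower the weight of the finding but do not remove it. The exploratory label is offered as the reason for having no power analysis; it does not settle which patients are analysed. Appendix B states a pooling rule, and that rule changes the analysed group.

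A reader might infer that the pooled result is biased, that Butler's patients are not Veterans, or that its allocation is unequal. The documents support none of these; they are silent on all three.

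**Conclusion.** The gap is real and should be closed, but it concerns the definition of the analysed group and the form of the comparison; bias has not been shown. As written, the pooled analysis does not answer Aims 1 and 2 for the forty PVAMC patients, and it permits a treatment comparison across two separately run studies.

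The size depends on facts not given. It is zero with equal Butler allocation. Under the assumed Butler n of 20 and a 0.8 SD difference in change, it is 0.07 SD at 12/8 with type I error of 4-5%, and 0.18 SD at 15/5 with type I error of about 8-10%. The splits, Butler's size, the study difference, the visit correlation and the 5% level are all assumptions. Confidence is medium for that reason. What does not depend on them is the mismatch between the aims and the analysed set.

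**What to change.** In Appendix B:
- Keep a study-of-origin column when the Butler rows are appended.
- Pool only randomised active-versus-sham Butler data, and state briefly Butler's size, eligibility, randomisation and allocation.

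In DATA ANALYSIS:
- Include study and study-by-time in any pooled repeated-measures or mixed model, or study as a factor when the outcome is a change score or a baseline-adjusted post-treatment score.
- Report the randomised VA-only estimate for Aims 1 and 2 beside the pooled one.
- State before the merge which is the main result. The choice is the sponsor's, though VA-only matches the aims as written.
- A treatment-by-study estimate is optional. If shown, fit it in a separate model and label it descriptive, given its imprecision.

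The cost is one spreadsheet column, a short description of the Butler study and a few sentences. At the assumed Butler n of 20, the study terms raise the treatment standard error by 0-3%. The VA-only standard error is 17-22% larger than the study-adjusted pooled one, which is the price of making VA-only the main result.
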